7.4.1.2 Dose Delay Criteria for Cabozantinib

Cabozantinib dosing should be delayed for the following:

- Urine protein/creatinine ratio (UPCR) > 2.0 *or* urine dipstick protein \geq 3+ *or* urine protein > 2.0 g / 24 hours. Obtain 24 hour urine protein prior to next dosing visit.
- Grade 3 prolonged QTc interval (ie, QTcF interval > 500 msec on at least 2 out of 3 separate ECGs performed at least 3 minutes apart)
- Any Grade 2 or 3 drug-related venous thrombosis requiring anticoagulation, with the following exception:
 - Any recurrent or worsening venous thromboembolic event after restarting cabozantinib will require discontinuation
- Any other Grade 2 drug-related adverse event or grade 2 drug-related laboratory abnormality (e.g., AST, ALT, total bilirubin) that persists for more than 1 week or worsens despite supportive care management, with the following exception:
 - Any Grade 2 drug-related hemorrhage requires dose delay
 - Grade \geq 2 arterial thromboembolic events, including cerebrovascular ischemia, cardiac ischemia/infarction, peripheral or visceral arterial ischemia, require discontinuation
- Sustained Grade 3 drug-related hypertension (systolic BP \geq 160 mm Hg or diastolic BP \geq 100 mm Hg). NOTE: Stopping or reducing the dose of cabozantinib is expected to cause a decrease in BP. The treating physician should monitor the participant for hypotension and adjust the number and dose of antihypertensive medications accordingly.
- Any other Grade 3 drug-related adverse event or laboratory abnormality, with the following exceptions:
 - Grade \geq 3 drug-related hemorrhage requires discontinuation ([Section 8.1.2](#)).
 - Drug-related AST or ALT > 8 x ULN requires discontinuation ([Section 8.1.2](#)).
 - Concurrent AST or ALT > 3 x ULN and total bilirubin > 2 x ULN, consistent with potential drug-induced liver injury (see [Section 9.2.7](#)), requires discontinuation ([Section 8.1.2](#))
 - Grade 3 drug-related amylase or lipase abnormalities that are not associated with symptoms or clinical manifestations of pancreatitis do not require dose delay. In such cases, more frequent monitoring (eg, weekly) of amylase and lipase is recommended. If amylase or lipase worsen to Grade 4 severity or the participant develops symptoms or clinical manifestations of pancreatitis, dosing should be delayed.

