7.4.1.3 Dose Delay Criteria for Sunitinib

Sunitinib dose delays should be based on instructions in the approved product label and should be considered for any severe or intolerable drug-related adverse events.

Within a cycle, missed doses of sunitinib should be skipped. Participants should never be dosed during the 2-week off period of each 6-week cycle, even if treatment delays occurred earlier in the cycle and therapy is ready to be resumed. If treatment is delayed past the end of the 6-week cycle, the start of the next cycle should be delayed until treatment with sunitinib resumes.

Prior to resuming therapy after a dose delay, refer to [Section 7.4.2](#) for dose reduction recommendations and [Section 8](#) for discontinuation criteria.

For this protocol, sunitinib dosing should be delayed for any of the following:

- Urine protein/creatinine ratio (UPCR) ≥ 2.0 or urine dipstick protein $\geq 3+$ or urine protein ≥ 2.0 g / 24 hours. Obtain 24 hour urine protein prior to next dosing visit.
- Grade 3 prolonged QTc interval (ie, QTcF interval > 500 msec on at least 2 out of 3 separate ECGs performed at least 3 minutes apart)
- Any Grade 2 or 3 drug-related venous thrombosis requiring anticoagulation, with the following exception:
 - Any recurrent or worsening venous thromboembolic event after restarting sunitinib will require discontinuation
- Any other Grade 2 drug-related adverse event that persists or worsens despite supportive care management, with the following exception:
 - Any Grade 2 drug-related hemorrhage requires dose delay
 - Grade ≥ 2 arterial thromboembolic events, including cerebrovascular ischemia, cardiac ischemia/infarction, peripheral or visceral arterial ischemia, require discontinuation
- Grade 3 drug-related hypertension (systolic BP ≥ 160 mm Hg or diastolic BP ≥ 100 mm Hg). NOTE: Stopping or reducing the dose of sunitinib is expected to cause a decrease in BP. The

treating physician should monitor the participant for hypotension and adjust the number and dose of antihypertensive medications accordingly.

- Any other Grade 3 drug-related adverse event or laboratory abnormality, with the following exceptions:
 - Grade \geq 3 drug-related hemorrhage requires discontinuation (Section 8.1.2).
 - Drug-related AST or ALT $>$ 8 x ULN requires discontinuation (Section 8.1.2).

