 - Concurrent AST or ALT $>$ 3 x ULN and total bilirubin $>$ 2 x ULN, consistent with potential drug-induced liver injury (see Section 9.2.7), requires discontinuation (Section 8.1.2)
 - Grade 3 drug-related amylase or lipase abnormalities that are not associated with symptoms or clinical manifestations of pancreatitis do not require dose delay. In such cases, more frequent monitoring (eg, weekly) of amylase and lipase is recommended. If amylase or lipase worsen to Grade 4 severity or the participant develops symptoms or clinical manifestations of pancreatitis, dosing should be delayed.
- Grade 4 drug-related amylase or lipase abnormalities require dose delay. Participants should be monitored for development of symptoms or clinical manifestations of pancreatitis.
- Grade 4 drug-related electrolyte abnormalities require dose delay. Electrolyte correction with supplementation/appropriate management should be promptly initiated.
- Grade 4 drug-related neutropenia, lymphopenia, leukopenia, anemia, or thrombocytopenia
- Any adverse event, laboratory abnormality, or intercurrent illness which, in the judgment of the investigator, warrants delaying sunitinib dosing
- For participants scheduled for major surgery, including dental surgery which may impact bone healing, sunitinib dosing should be delayed at least 28 days prior to scheduled surgery. The treating physician should use clinical judgment with regard to the risks and benefits of the planned surgical procedure if it is not possible to delay sunitinib dosing for 28 days prior to the procedure. A delay of sunitinib dosing of 5 to 7 days is recommended for healing for minor surgery.

As a general approach, all AEs related to sunitinib should be managed with supportive care when possible at the earliest signs of toxicity. Calcium, magnesium, potassium, and phosphorus should be kept above the lower limits of the laboratory normal values. Please refer to the sunitinib approved product label and Appendix 10 for additional information regarding AE monitoring and management.

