7.4.2.3 Dose Reduction and Escalation for Sunitinib

Sunitinib Dose Reductions are permitted as per the approved product label for safety reasons or when a concomitant strong CYP3A4 inhibitor is needed (Appendix 9). Selection of an alternative

concomitant medication with minimal or no enzyme inhibition potential is recommended whenever possible.

After toxicity requiring a dose delay has improved and meets the criteria to resume dosing (Section 7.4.3.3), participants should resume sunitinib at one dose level reduction. Dose reductions should occur in 12.5 mg decrements. No more than 2 dose reductions are allowed. If more than 2 dose reductions are necessary (ie, reduction to less than 25 mg daily), the participant must be permanently discontinued (Section 8.1.3).

Participants who required a dose delay due to Grade 3 hypertension, which improved with antihypertensive medications, or any Grade 2 or 3 drug-related adverse event or asymptomatic laboratory abnormality that improved to Grade ≤ 1 within 7 days with supportive medical care may resume sunitinib at the same dose or a reduced dose, at the discretion of the investigator.

At the time a dose reduction is considered, also refer to Section 7.4.2.3 for dose delay recommendations and Section 8.1.3 for discontinuation criteria.

Sunitinib Dose Escalations are permitted as per the approved product label when a concomitant CYP3A4 inducer is needed (Appendix 9). Selection of an alternative concomitant medication with minimal or no enzyme induction potential is recommended whenever possible.

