7.4.3.3 Criteria to Resume Sunitinib Treatment

Within a cycle, missed doses of sunitinib should be skipped and not replaced. Participants should never be dosed during the 2-week off period of each 6-week cycle, even if treatment delays occurred earlier in the cycle and therapy is ready to be resumed. If treatment is delayed past the end of the 6-week cycle, the start of the next cycle should be delayed until treatment with sunitinib resumes.

Participants may resume treatment with sunitinib when the drug-related AE(s) resolve to Grade \leq 1 or baseline value, with the following exceptions:

- Participants may resume dosing in the presence of Grade 2 fatigue
- Participants who delayed dosing due to prolonged QTcF may resume dosing at one reduced dose level once QTcF returns to \leq 500 msec
- Participants who delayed dosing due to UPCr \geq 2.0 or urine dipstick protein \geq 3+ may resume dosing at one dose level reduction when 24 hour urine protein $<$ 2.0 g
- Participants who delayed dosing due to Grade 3 hypertension may resume dosing at the same dose or at one dose level reduction, at the discretion of the investigator, when hypertension has improved to Grade \leq 2
- Participants who delayed dosing due to Grade 4 lipase or amylase abnormalities may resume dosing upon resolution to Grade \leq 2
- Participants who develop a pulmonary embolism and/or DVT should have study treatment interrupted until therapeutic anticoagulation is established. Treatment with cabozantinib may be resumed in subjects with pulmonary embolism or DVT if it is determined that the event is uncomplicated and that the subject is deriving clinical benefit from cabozantinib treatment and that anticoagulation does not place them at a significant risk that outweighs the benefit of resuming treatment per discretion of the investigator.
- Participants who delayed dosing due to \leq Grade 2 hemorrhage may resume dosing if bleeding is under control (recovered to at least Grade 1 level) and has a low risk of recurrence
- If treatment is delayed $>$ 6 weeks for any reason, the participant must be permanently discontinued from study therapy, except in cases where permission to resume treatment is granted by the BMS Medical Monitor or designee.

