8.1.3 Sunitinib Dose Discontinuation

Treatment with sunitinib should be permanently discontinued for any of the following:

- Any requirement for more than 2 sunitinib dose reductions (ie, reduction to less than 25 mg daily)
- Any Grade drug-related arterial thrombosis.
- Grade 4 drug-related hemorrhage or recurrent Grade 3 drug-related hemorrhage after dose reduction.
- Grade 4 drug-related symptomatic venous thrombosis.
- Grade 4 drug-related cardiac toxicity.
- Grade 4 hypertension or persistent Grade 3 hypertension despite optimal medical management and sunitinib dose reduction
- Any drug-related liver function test (LFT) abnormality that meets the following criteria requires discontinuation:
 - AST or ALT > 8 x ULN.
 - Concurrent AST or ALT > 3 x ULN and total bilirubin >2 x ULN, consistent with potential drug-induced liver injury (see [Section 9.2.7](#)).
- Any other Grade 4 drug-related adverse event or laboratory abnormality, with the following exceptions:

- Grade 4 neutropenia \leq 7 days
- Grade 4 lymphopenia or leukopenia
- Grade 4 amylase or lipase abnormalities that are not associated with symptoms or clinical manifestations of pancreatitis
- Isolated Grade 4 electrolyte abnormalities that are not associated with clinical sequelae and are corrected with supplementation/appropriate management within 72 hours of their onset
- Any dosing interruption lasting $>$ 6 weeks unless the BMS Medical Monitor or designee is consulted and agrees with the rationale for resuming therapy after a delay $>$ 6 weeks. Note that tumor assessments should continue as per protocol even if dosing is interrupted.
- Any adverse event, laboratory abnormality, or intercurrent illness which, in the judgment of the Investigator, presents a substantial clinical risk to the participant with continued sunitinib dosing.

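### Protocol 7.4.1.3 and 8.1.3 give conflicting sunitinib rules for a first Grade 3 drug-related hemorrhage, and nothing says which governs

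*Protocol*

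**What the plan says.** Two places in the protocol set a stop rule for hemorrhage on sunitinib.

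- **7.4.1.3 (dose delay).** Grade 3 drug-related events generally lead to a delay. Hemorrhage is listed as an exception: Grade ≥ "3 drug-related hemorrhage requires discontinuation (Section 8.1.2"). The cited section, 8.1.2, is the cabozantinib list.
- **8.1.3 (sunitinib discontinuation).** The hemorrhage item reads "Grade 4 drug-related hemorrhage or recurrent Grade 3 drug-related hemorrhage after dose reduction".

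Three further texts bear on what a site does next.

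- **Pointers to the stopping criteria.** 7.4.1.3 says "Prior to resuming therapy after a dose delay, refer to" 7.4.2 for reductions and Section 8 for stopping criteria. 7.4.2.3 tells the reader, when a reduction is considered, to "also refer to Section 7.4.2.3 for dose delay recommendations and Section 8.1.3 for discontinuation criteria".
- **7.4.3.3 (resumption).** The lead sentence allows sunitinib to resume once drug-related events are back to Grade 1 or baseline. A separate bullet says that participants delayed for ≤ "Grade 2 hemorrhage may resume dosing if bleeding is under control (recovered to at least Grade 1 level"), provided recurrence is unlikely.
- **7.4.2.3 (reduction).** After a delay the usual course is to resume one dose level lower. Where a Grade 2 or 3 drug-related event has settled to Grade 1 or less within 7 days, the investigator may instead keep the same dose.

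**The concern.** A first Grade 3 drug-related bleed in Arm C has two prescribed outcomes. Under 7.4.1.3 sunitinib stops. Under 8.1.3 no stop is required, and the phrase about recurrence after dose reduction makes sense only if the participant went back on drug after the first bleed.

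At stake is the safety of a participant who has had a severe hemorrhage. Section 9 of the protocol allows no waivers and calls adherence essential, so sites need a single instruction. There is also a smaller reporting consequence. Adverse events leading to discontinuation are part of the secondary safety endpoint (Protocol Table 4-1) and are tabulated by arm (SAP 7.6.3). If sites follow different rules, the same event could be counted as a discontinuation at one site and not at another.

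**Working it through.** The check is a comparison of texts. The plan states no figure to reproduce and no formula applies.

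**Step 1. Apply each sunitinib rule to the same event, a first Grade 3 drug-related hemorrhage.**

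| Section | Rule for hemorrhage | Result for a first Grade 3 bleed |
|---|---|---|
| 7.4.1.3 | Discontinue at Grade 3 or higher | Stop |
| 8.1.3 | Discontinue at Grade 4, or at Grade 3 recurring after a reduction | No stop required |

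For sunitinib the count is 1 against 1. At Grade 4 the two agree.

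**Step 2. See whether another item in 8.1.3 closes the gap.** The list has 10 items: more than 2 dose reductions; arterial thrombosis; hemorrhage; venous thrombosis; cardiac toxicity; hypertension; liver tests; other Grade 4 events; interruption beyond 6 weeks; investigator judgment. None stops sunitinib for a first Grade 3 bleed as such. Three could reach it, each on a further condition: the need for a third reduction, an interruption beyond 6 weeks without agreement to resume, or the investigator's view that the event "presents a substantial clinical risk to the participant with continued sunitinib dosing". The last is discretionary.

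**Step 3. See whether the resumption rules settle it.** The hemorrhage bullet in 7.4.3.3 addresses Grade 2 or lower, which is consistent with 7.4.1.3. It does not say that resumption is confined to those grades. The lead sentence of 7.4.3.3 covers drug-related events generally, and the 7-day sentence in 7.4.2.3 covers any Grade 2 or 3 drug-related event. Neither excludes a resolved Grade 3 bleed.

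**Step 4. Trace what a site relying on 8.1.3 could do.** For a participant on 50 mg, a one-level reduction gives 50 − 12.5 = 37.5 mg, as in Table 7.4.2-1. If the bleed settled to Grade 1 or less within 7 days, the sentence in 7.4.2.3 read alone would also allow 50 mg again.

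**Step 5. Check the cross-references.** 7.4.1.3 cites 8.1.2 three times: once for hemorrhage and twice for liver tests, for example "requires discontinuation (Section 8.1.2"). For the liver tests 8.1.2 and 8.1.3 carry the same thresholds, so correcting those references changes nothing. Correcting the hemorrhage reference alone would point the Grade 3 stop at the looser item in 8.1.3. Separately, 7.4.2.3 cites itself for dose delay where 7.4.1.3 is evidently meant. These reference errors do not alter treatment by themselves, because 7.4.1.3 states its own rule.

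**The case against.** The strongest reply is that absence from 8.1.3 is not permission. The protocol splits mandatory stops between the delay sections and the discontinuation sections. For example, 7.4.1.3 requires a stop for venous thromboembolism that recurs or worsens after restarting sunitinib, and 8.1.3 has no matching item. A site that follows 7.4.1.3 breaches nothing, and a site that follows the pointer from 7.4.1.3 to Section 8 has the Grade 3 stop in front of it. This stands as far as omission goes, and it is why the zero-of-10 count proves little alone. It does not dispose of the conflict, because the hemorrhage item in 8.1.3 is not silent: its wording presupposes re-treatment. The pointer in 7.4.2.3 also names 8.1.3 directly.

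A second reply is that 7.4.1.3 may be the mistake. It largely repeats the cabozantinib section, down to the 8.1.2 references, whereas 8.1.3 has items of its own for sunitinib. The protocol also ties sunitinib delays and reductions to a product label that is not among the documents. This also stands. It means the direction of the correction is open, not that no correction is needed.

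A reader might go further and infer that the stricter rule is plainly the intended one. Two arguments invite that. First, cabozantinib stops at Grade ≥ "3 drug-related hemorrhage requires discontinuation ([Section 8.1.2"), and 8.1.2 agrees, so three of four hemorrhage rules for the oral drugs point the same way. But two of those govern a different drug in the other arm. Second, 7.4.3.3 might be read as permitting resumption only after Grade 2 or lower. The section does not say that, and its general sentence is wider.

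**Conclusion.** The inconsistency is real and confined to one event: a first Grade 3 drug-related hemorrhage on sunitinib. One sunitinib rule requires a stop, the other implies re-treatment, and nothing in the documents reconciles them or says which prevails. It should be corrected because a site acting on the section titled for sunitinib discontinuation could give the drug again after a severe bleed.

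The size in participants is unknown. The documents give no hemorrhage rate, so any number would be a guess. The effect on the discontinuation tables is a possibility that follows from sites reading different sections; it has not been shown. A reader might also infer a threat to the efficacy comparison. The documents do not support that: the conflict concerns safety management in Arm C, and the planned PFS and OS analyses, sample size and error rates are unaffected.

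The conclusion rests on the text as published. It assumes only that no sponsor instruction outside these documents has already told sites which rule to use.

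**What to change.** The sponsor states which hemorrhage rule governs sunitinib and aligns the sections in one amendment.

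**Default: the stricter rule**, because stopping satisfies both sections as they stand.

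1. In 8.1.3, replace the hemorrhage item with a stop for drug-related hemorrhage of Grade 3 or higher, first occurrence included.
2. In the same amendment, change the three references in 7.4.1.3 from 8.1.2 to 8.1.3. This should not be done without step 1.
3. In 7.4.2.3, state that events requiring discontinuation are excluded from the sentence on resuming at the same or a reduced dose, and correct the self-reference to 7.4.1.3.

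**If the sponsor confirms that 8.1.3 is intended**, carry its hemorrhage wording into 7.4.1.3 and add to 7.4.3.3 an explicit condition for resuming at a reduced dose after a first Grade 3 bleed. The same-dose option in 7.4.2.3 should then exclude that event, and the references in 7.4.1.3 should still move to 8.1.3.

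Either route edits three sections (7.4.1.3, 7.4.2.3 and 8.1.3, or 7.4.1.3, 7.4.2.3 and 7.4.3.3) and needs a notice to sites. Neither needs new data collection or a change to the analysis. While the amendment is open, the two sunitinib lists should also be compared on arterial events, where 7.4.1.3 stops at Grade 2 or higher and 8.1.3 at any grade, and on recurrent venous events.

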8.1.4 Treatment Beyond Disease Progression

Accumulating evidence indicates a minority of participants treated with immunotherapy or anti-angiogenic therapy may derive clinical benefit despite initial evidence of PD.^{19,51,52}

Participants, regardless of study arm, will be permitted to continue treatment beyond initial RECIST 1.1 defined PD, assessed by the investigator, up to a maximum of 24 months from the date of first dose, as long as they meet the following criteria:

- Investigator-assessed clinical benefit
- Tolerance of study drug
- Stable performance status
- Treatment beyond progression will not delay an imminent intervention to prevent serious complications of disease progression (eg, CNS metastases)
- Participant provides written informed consent prior to receiving additional treatment with the study drug regimen. All other elements of the main consent including description of reasonably foreseeable risks or discomforts, or other alternative treatment options will still apply.

A radiographic assessment/ scan should be performed within 6 weeks of initial investigator-assessed progression to determine whether there has been a decrease in the tumor size or continued PD. The assessment of clinical benefit should be balanced by clinical judgment as to whether the participant is clinically deteriorating and unlikely to receive any benefit from continued treatment with nivolumab.

If the investigator feels that the participant continues to achieve clinical benefit by continuing treatment, the participant should remain on the trial and continue to receive monitoring according to the Schedule of Activities Schedule in [Section 2](#). Treatment may be continued beyond investigator-assessed progression if the investigator confirms that the participant meets the criteria specified in [Section 8.1.4](#).

For the participants who continue study therapy beyond progression, further progression is defined as an additional 10% increase in tumor burden with a minimum 5 mm absolute increase from time of initial PD. This includes an increase in the sum of diameters of all target lesions and/ or the

diameters of new measurable lesions compared to the time of initial PD. It is recommended that study treatment should be discontinued permanently upon documentation of further progression.

New lesions are considered measureable at the time of initial progression if the longest diameter is at least 10 mm (except for pathological lymph nodes which must have a short axis of at least 15 mm). Any new lesion considered non-measureable at the time of initial progression may become measureable and therefore included in the tumor burden if the longest diameter increases to at least 10 mm (except for pathological lymph nodes which must have a short axis of at least 15 mm). In situations where the relative increase in total tumor burden by 10% is solely due to inclusion of new lesions which become measurable, these new lesions must demonstrate an absolute increase of at least 5 mm.

